## Project Protocol

### Experimental design

The study consists of a mechanistic randomized placebo-controlled clinical trial with a mixed experimental design, whose objective is to assess which variables that have been linked to central sensitization (CS) in chronic pain patients can predict the response of chronic low back pain (CLBP) patients to spinal manipulative therapy (SMT). In order to do this, clinical, psychophysical and inflammatory variables will be measured in CLBP patients, which will be exposed to either SMT or a placebo SMT for 12 visits over a 4-week period. Another group made up of healthy volunteers will be used to determine the reference values of the same variables in a healthy population and compare them with the clinical population, before and after exposure. The primary outcome measures and main clinical variables are pain intensity and disability. All variables will be measured before the first SMT session, as well as at the end of the twelfth and last session, except for pain intensity, which will be measured at the start of each session for exploratory reasons.

**Figure 1.** Study protocol for the clinical trial

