### **Sample size calculation**

To determine the ideal number of participants, we have considered our first aim, which is to identify the variables linked to the CS phenotype that could help predict the response to treatment based on SMT for CLBP. In order to do this, we will perform a multiple regression analysis, using five independent variables as predictors, in particular the score on the pain catastrophizing scale (PCS) and central sensitization inventory (CSI) questionnaires (indicators of catastrophism and CS), the pressure pain thresholds (PPTs) in the primary pain area (marker of primary hyperalgesia), the urinary levels of the cytokine Tumor Necrosis Factor Alpha (TNF- $\alpha$ ; marker of inflammation) and finally the expectations of relief for each patient (indicative of potential placebo effects). The baseline values of these variables will be included in the multiple regression model. For each predictor variable, it is recommended to estimate about ten sample elements, therefore we predict that a sample size of 50 patients per group will be necessary (Ortega Calvo and Cayuela Dominguez, 2002). Taking into account two groups, one that will receive real SMT and the other placebo SMT, we will need a sample of 100 patients. An additional group of age and sex-matched healthy individuals without CLBP of the same size (50 participants) will be recruited to be used as a reference group, to determine

reference values in a healthy population for the predictor variables (questionnaires, PPTs, cytokines only)

Regarding the two main outcome variables (pain intensity and disability related to low back pain), we expect a reduction in pain and disability after one month in patients who receive 12 sessions of SMT compared to placebo. We aim to detect small to moderate effects since it is a one-month intervention in patients with chronic pain unresolved by other treatments over at least 3 months. Therefore, based on an effect size of  $f = 0.175$ , an alpha of 0.05, a power of 0.8 for 2 groups and 2 repeated measures (baseline and session 12), and a correlation between the repeated measures of 0.5, the size of the necessary sample is 34 patients per group and a total of 68 patients to detect statistically significant changes in clinical pain and disability. Therefore, our analysis based on the regression model to predict the clinical course provides us with a large enough size for both the first and second aims of this study.

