In order to interpret the values obtained in patient groups, they will be compared with reference values obtained from the healthy controls to both CLBP groups. This will allow characterizing the patient groups to determine whether they show increased psychological symptoms, increased pain sensitivity and hyperalgesia as well as increased TNF-alpha levels compared with a reference healthy population. In order to do this, a series of mixed analyses of variance will be performed to examine differences in PPTs, urinary TNF- α levels, PCS, CSI, BDI-II and GAD scores before and after treatment between the three groups (control, SMT and placebo). To test a priori hypotheses, significant effects will be decomposed using planned comparisons. For the rest of the effects, Tukey's HSD will be used for testing any pair-wise comparisons between group means.

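### The SAP asks whether patients differ from healthy people but names no baseline patient-versus-healthy contrast; its averaged group effect understates that gap if patients improve.

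*SAP*

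**What the plan says.** The closing paragraph of the SAP's Statistical analyses gives the healthy comparison the purpose of "characterizing the patient groups to determine whether they show increased psychological symptoms, increased pain sensitivity and hyperalgesia as well as increased TNF-alpha levels", relative to a healthy population. For this, "a series of mixed analyses of variance will be performed" on PPTs, urinary TNF-alpha, PCS, CSI, BDI-II and GAD, "before and after treatment between the three groups (control, SMT and placebo"). For a priori hypotheses, "significant effects will be decomposed using planned comparisons"; for all other effects, "Tukey's HSD will be used for testing any pair-wise comparisons between group means". The planned comparisons are not listed. No contrast is confined to baseline, and none combines the two patient arms.

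The Protocol (Experimental design) says the healthy values will be used to "compare them with the clinical population, before and after exposure". Under Sample size calculation it states "we will need a sample of 100 patients", 50 per arm, plus 50 healthy volunteers. Under Independent variables, the volunteers receive no intervention over the 4 weeks. Under Healthy population sample, they are matched on age and sex to the SMT arm.

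**The concern.** Patients are untreated only at the first visit. By session 12 they have had 12 real or sham sessions, while the controls have had nothing. A group effect taken over both visits is therefore not the difference between untreated patients and healthy people. If patients improve, it is smaller.

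The other route to a baseline comparison is a significant group-by-time interaction followed by decomposition. Improvement dilutes the group effect, yet the test that would release the baseline comparison may miss that same improvement. Because the planned comparisons are not listed, the choice of contrast also stays open until the data are seen.

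At stake is the statement that these patients show heightened sensitivity, symptoms and TNF-alpha. That statement frames the trial's reading of central sensitization, although it is not the efficacy result.

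**Working it through.** **The plan's own power figure.** It concerns SMT versus placebo, not the healthy comparison. With f = 0.175, two groups, two visits and correlation 0.5, λ = f²·N·2/(1 − ρ). At N = 68, λ = 0.030625 × 68 × 2 / 0.5 = 8.33, and the power of F(1, 66) is 0.81. The minimum N is 67, so 68 for equal groups: the stated figure reproduces. No power figure is given for the healthy comparison.

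**Inputs.** From the Protocol: 50 + 50 patients, 50 controls, α = 0.05. Assumed: SD 1; a baseline gap d in the direction of worse status, equal in both arms; an improvement c in both arms; no change in controls. The Protocol states ρ = 0.5 for pain and disability only, so applying it here is an assumption, with a range of 0.5 to 0.8.

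**Baseline, d = 0.5.**
- Pooled 100 v 50: SE = √(1/100 + 1/50) = 0.173; 0.5/0.173 = 2.89; power 0.82.
- Three-group omnibus: λ = 50 × (2/3) × d² = 33.3 × 0.25 = 8.33; power 0.73.
- One arm v controls by Tukey (critical value 2.37): SE = √(1/50 + 1/50) = 0.200; 0.5/0.200 = 2.50; power 0.55.
- A pooled contrast inside the three-group model keeps 0.82. The loss comes from the omnibus or Tukey route, not from having three groups.

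**Group effect over two visits.** The gap becomes d − c/2, with variance (1 + ρ)/2 = 0.75 at ρ = 0.5. The omnibus λ is 33.3 × (d − c/2)²/0.75, and the pooled contrast has noncentrality (d − c/2)/(0.866 × 0.173).

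| d = 0.5, ρ = 0.5 | Averaged gap | Omnibus | Pooled contrast |
|---|---|---|---|
| c = 0 | 0.50 | λ = 11.11, power 0.85 | 3.33, power 0.91 |
| c = 0.4 | 0.30 | λ = 4.00, power 0.41 | 2.00, power 0.51 |

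**Group-by-time test.** The variance of a change score is 2(1 − ρ) = 1 at ρ = 0.5, so λ = 33.3c². For c = 0.3, λ = 3.00 and power is 0.32. For c = 0.4, λ = 5.33 and power is 0.52. A higher correlation helps this test: at c = 0.4, ρ = 0.8 gives λ = 33.3 × 0.16/0.4 = 13.33 and power 0.91.

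**Milder, unequal improvement.** Suppose the gap closes by 50% under SMT and 25% under placebo. The averaged effect keeps (0.75 + 0.875)/2 = 81% of the gap. At d = 0.5 and ρ = 0.5, power is 0.68 for the omnibus test and 0.77 for a pooled contrast on the averaged values, and the interaction has 0.18.

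**Break-even.** An averaged pooled contrast matches the baseline one when the share of the gap retained equals √((1 + ρ)/2). That is a mean closing of the gap of 27% at ρ = 0.5, 16% at 0.7 and 10% at 0.8.

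**Size of the gap.** At d = 0.4, baseline power is 0.63 pooled, 0.52 omnibus and 0.36 per Tukey pair. At d = 0.8 it is 0.996, 0.99 and 0.95.

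**The case against.** Four points can fairly be made for the plan.

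- **The question is not only about baseline.** The Protocol asks for the comparison before and after exposure, and controls are measured twice for that reason. A three-group, two-visit ANOVA fits that purpose. This stands: the ANOVA should stay, and the gap concerns only the characterisation aim.
- **Planned comparisons could include the right contrast.** Raised symptoms, sensitivity and TNF-alpha read as an a priori hypothesis, which the SAP sends to planned comparisons rather than Tukey. A reader might infer that each arm will necessarily be set against controls by Tukey pairs; the SAP does not clearly say so. This stands too. The contrast is nevertheless unlisted and conditional on a significant effect.
- **Loss of power is not certain.** A reader might infer that averaging always costs power. It does not: with no change in patients, both averaged tests (0.85 and 0.91) beat the baseline contrast (0.82), and with a large gap the cost of splitting the arms is small.
- **Improvement is assumed.** The Protocol expects reductions in pain and disability and says TNF-alpha may respond, but gives no expected change for any variable in this comparison. A reader might also invoke regression to the mean; the documents do not establish it, since eligibility sets no threshold on these variables.

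Baseline means by group can still be reported whatever the omnibus test shows. That gives a description, not a pre-specified test of the claim.

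**Conclusion.** The point holds in a limited form. The SAP sets out to "determine whether they show increased psychological symptoms, increased pain sensitivity and hyperalgesia" but pre-specifies no test that isolates the untreated difference. If patients improve, the averaged group effect understates that difference by half the mean improvement, whatever the correlation or sample size: with a 0.5 SD gap and a 0.4 SD improvement, 0.30 SD is shown.

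The cost in power is conditional on that improvement, on the size of the gap and on the correlation. The 82%, 41% and 52% figures rest on assumed values, and the 0.4 SD improvement is a demanding case that closes 80% of the gap.

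This is a reference analysis without a power target. The primary SMT-versus-placebo comparison is unaffected. It is an improvement available at no data cost, not a flaw in the trial's main result.

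**What to change.** In the SAP's closing paragraph, pre-specify for each variable one baseline contrast: all CLBP patients (SMT plus placebo, n = 100) versus healthy volunteers (n = 50). State that it is the test of the characterisation claims and does not depend on any omnibus or interaction result. Adjust it for age and sex, because the controls are matched only to the SMT arm and pooling brings in the placebo arm. Keep the three-group mixed ANOVA for the before-and-after question. The cost is a change of SAP wording: the baseline measurements are already planned, and matching already requires age and sex.
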